6.1.2. Study Period

Table AMAG.6.2 defines the study periods.

Table AMAG.6.2. Study Periods

Period	Start Date	End Date
Study Baseline	Informed Consent date	Prior to Visit 2 dose date/time. If dose date is missing, the last date at Visit 2 will be used.
Period 1 (Weeks 0-12)	After Study Baseline end date.	Prior to Visit 8 dose date/time or the date of the ETV (if it occurs between Visits 2 and 8). If dose date is missing, the last date at Visit 8 will be used.
Period 2 (Weeks 12-52)	After Period 1 end date.	Prior to Visit 18 dose date/time or the date of the ETV (if it occurs between Visits 8 and 18). If dose date is missing, the last date at Visit 18 will be used.
Period 3 (Weeks 52-104)	Only for subjects with Clinical Benefit: After Period 2 end date.	Visit 31 dose date or the date of the ETV (if it occurs between Visits 18 and 31). If dose date is missing, the last date at Visit 31 will be used.
Follow-up (Weeks 104-120)	
 • Subjects completed treatment and Period 3: After Period 3 end date. • Subjects discontinued treatment in Period 2 but completed Period 2: After Period 2 end date. • Subjects with no Clinical Benefit and did not enter Period 3: After Period 2 end date. • Subjects discontinued treatment in Period 3 but completed Period 3: After Period 3 end date. 	Visit 804 dose date or the date of the ETV (if it occurs between Visits 801 and 804), whichever is earliest.

Abbreviation: ETV = early termination visit.

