	4a.2) Treatment-Emergent Abnormal Labs and Vital Signs	
Randomized to LY at Period 1: Baseline will be all scheduled and unscheduled measurements recorded during the baseline period as defined above (4a.1). If time is not collected for a measurement taken on Visit 2 dose date, it will be assumed that it occurred prior to first dose.
 
Randomized to Placebo at Period 1: The last non-missing assessment (scheduled or unscheduled) recorded prior to the first dose of Period 2 LY study treatment. If time is not collected for a measurement taken on Visit 8 dose date, it will be assumed that it occurred prior to first dose.
	
Randomized to LY at Period 1: LY Treatment Period will be defined as above (4a.1). All scheduled and unscheduled measurements will be included.
 
Randomized to Placebo at Period 1: LY Treatment Period will be defined as above (4a.1). All scheduled and unscheduled measurements will be included.

Baseline and Postbaseline Definitions for Safety Analyses

Safety Group	Analysis Type	Baseline (Periods as defined in Table AMAG.6.2)	Postbaseline (Periods as defined in Table AMAG.6.2)
	4a.3) Change from Last Baseline to Week xx and to Last Postbaseline for Labs and Vital Signs	
Randomized to LY at Period 1: The last scheduled non-missing assessment recorded prior to the date of first dose of study treatment during the baseline period defined above (4a.1). If time is not collected for a measurement taken on Visit 2 dose date, it will be assumed that it occurred prior to first dose.
 
Randomized to Placebo at Period 1: The last non-missing scheduled assessment recorded prior to the first dose of Period 2 study treatment. If time is not collected for a measurement taken on Visit 8 dose date, it will be assumed that it occurred prior to first dose.
	
Randomized to LY at Period 1: LY Treatment Period will be defined as above (4a.1). Only scheduled measurements will be included. The ETVs are considered scheduled visits.
 
Randomized to Placebo at Period 1: LY Treatment Period will be defined as above (4a.1). Only scheduled measurements will be included. The ETVs are considered scheduled visits.

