Safety Population All LY (b) [All treatment periods where LY (IV or SC) is administered and Follow-Up]	4b.1) Treatment-Emergent Adverse Events	
Randomized to LY at Period 1: The baseline period is defined as the Study Baseline period. If time is not collected for an event starting on Visit 2 dose date, it will be assumed that it occurred after first dose.
 
Randomized to Placebo at Period 1: An ongoing event at the time of the first dose of Period 2 study treatment of LY. If time is not collected for an event starting on Visit 8 dose date, it will be assumed that it occurred after first dose.
	
Randomized to LY at Period 1: LY Treatment Period: starts at Period 1 Start Date and ends at Week 120 (Visit 804). Note that this will include the period after discontinuing treatment.
 
Randomized to Placebo at Period 1: LY Treatment Period: starts at the administration of the first dose of Period 2 study treatment of LY and ends at Week 120 (Visit 804). Note that this will include the period after discontinuing treatment.

Baseline and Postbaseline Definitions for Safety Analyses

Safety Group	Analysis Type	Baseline (Periods as defined in Table AMAG.6.2)	Postbaseline (Periods as defined in Table AMAG.6.2)
	4b.2) Treatment-Emergent Abnormal Labs and Vital Signs	
Randomized to LY at Period 1: Baseline will be all scheduled and unscheduled measurements recorded during the baseline period as defined above (4b.1). If time is not collected for a measurement taken on Visit 2 dose date, it will be assumed that it occurred prior to first dose.
 
Randomized to Placebo at Period 1: The last non-missing assessment (scheduled or unscheduled) recorded prior to the first dose of Period 2 LY study treatment. If time is not collected for a measurement taken on Visit 8 dose date, it will be assumed that it occurred prior to first dose.
	
Randomized to LY at Period 1: LY Treatment Period will be defined as above (4b.1). All scheduled and unscheduled measurements will be included.
 
Randomized to Placebo at Period 1: LY Treatment Period will be defined as above (4b.1). All scheduled and unscheduled measurements will be included.

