- Outlier/shift displays focusing on low values: A scatter plot, a shift table, and a shift to low table will be created. Unplanned measurements will be included. The scatter plot will plot the minimum value during the baseline period versus the minimum value during the treatment period. The shift table will include the number and percentage of subjects within each baseline category (minimum value is low, normal, high, or missing) versus each postbaseline category (minimum value is low, normal, high, or missing) by treatment. Subjects in the Safety Population will be included in the shift table. The shift from normal/high to low table will include the number and percentage of subjects by treatment whose minimum baseline result is normal or high and whose minimum treatment result is low. Subjects whose minimum baseline result is normal or high and have at least one result during the treatment period are included. The Fisher's exact test will be used to compare percentages of subjects who shift from normal/high to low between all Period 1 LY dose regimens (200 mg IV, 600 mg IV, 1000 mg IV) combined and placebo for Safety Population Period 1.
- Outlier/shift displays focusing on high values: The same approach described for low values will be used, except maximum values will replace minimum values.

Box plots will be displayed for Safety Population Period 1. Spaghetti plots will be explored to evaluate individual subject trends over time across the whole study. The summary of treatment-emergent abnormal, high, or low laboratory results at any time will be provided for Safety Population Period 1, Safety Population Period 2, Safety Population All SC LY, and Safety Population All LY.

For laboratory analyte measurements, a listing of abnormal findings will be created. The listing will include subject ID, treatment group, laboratory collection date, analyte name, and analyte finding.

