6.14.4. Vital Signs and Physical Characteristics

As described in Section 6.14.3, some of the analyses below may be incorporated into interactive display tools instead of or in addition to a static display. As such, the box plots for changes from baseline and the shifts to low/high summaries will be presented in a static display; the box plots for observed values, scatter plots and shift tables will be reviewed, if necessary, as an interactive display.

The following will be conducted for vital signs and physical characteristics (systolic blood pressure [BP], diastolic BP, pulse, weight, BMI):

- Box plots for observed values: To be created as described in Section 6.14.3 for laboratory analyte measurements.
- Box plots for change values: To be created as described in Section 6.14.3 for laboratory analyte measurements.
- Outlier/shift displays focusing on low values: To be created as described in Section 6.14.3 for laboratory analyte measurements, except the definition of treatment-emergent includes a threshold for change in addition to a limit as described in [Table AMAG.6.12](#). A treatment-emergent low result is defined as a change from a value

greater than or equal to the low limit at all baseline visits to a value less than the low limit at any time that meets the specified change criteria during the treatment period. The denominator will be subjects whose values are greater than or equal to the low limit at all baseline visits. To assess decreases, change from the minimum value during the baseline period to the minimum value during the treatment period will be used.

- Outlier/shift displays focusing on high values: The same approach described for low values will be used, except to assess increases, maximum values will replace minimum values. High limits will replace low limits.

Box plots will be displayed for Safety Population Period 1. Spaghetti plots will be explored to evaluate individual subject trends over time across the whole study. The summary of treatment-emergent high or low vital signs results at any time will be provided for Safety Population Period 1, Safety Population Period 2, Safety Population All SC LY, and Safety Population All LY.

Table AMAG.6.12. Categorical Criteria for Abnormal Treatment-Emergent Blood Pressure and Pulse Measurement, and Categorical Criteria for Weight and Changes for Adults

Parameter	Low	High
Systolic BP (mm Hg)	≤ 90 and decrease from baseline ≥ 20	≥ 140 and increase from baseline ≥ 20

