- The percentages of subjects with a total bilirubin measurement greater than or equal to 2 times (2X) the performing lab ULN during the treatment period will be summarized for all subjects with a postbaseline value, and subset into 4 subsets:
 - subjects whose non-missing maximum baseline value is less than or equal to 1X ULN
 - subjects whose maximum baseline is greater than 1X ULN but less than 2X ULN
 - subjects whose maximum baseline value is greater than or equal to 2X ULN
 - subjects whose baseline values are missing

Maximum baseline will be the maximum non-missing observation in the baseline period. The maximum value will be the maximum non-missing value from the treatment period. Planned and unplanned measurements will be included.

These analyses will be conducted for Safety Population Period 1, Safety Population Period 2, Safety Population All SC LY, and Safety Population All LY.

Individual graphical subject profiles will be prepared for subjects with an ALT or AST measurement greater than or equal to 5X ULN or with an alkaline phosphatase (ALP) measurement greater than or equal to 2X ULN. A graphical subject profile will be created for any subject meeting the criteria from the Safety Population (any phase, any medication). The graphical subject profile will include demographics, disposition, and a display of study drug exposure, AEs, medications, and liver-related measurements over time. The review for these subjects includes an assessment of the proximity of any ALT or AST elevation to any total bilirubin elevation, ALP levels, gamma-glutamyl transpeptidase (GGT) levels, other potential causes, and the temporal association with events such as nausea, vomiting, anorexia, abdominal pain, or fatigue.

A plot of maximum postbaseline ALT versus maximum postbaseline total bilirubin will be created that includes all subjects from the Safety Population (any phase, any medication). Each subject with at least 1 postbaseline ALT and total bilirubin contributes 1 point to the plot. The maximum ALT measurement divided by ULN and the maximum total bilirubin measurement divided by ULN during the treatment period are used. The measurements do not need to be taken at the same blood draw. Symbols will be used to indicate treatments (concentrated when multiple treatments are taken).

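### The pooled All LY column judges treatment-emergent abnormal laboratory and vital-sign results against all baseline values for LY-randomised subjects but only the last pre-LY value for ex-placebo subjects

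*SAP*

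**What the plan says.** The All LY safety population contains everyone who received at least one dose of LY. It therefore joins subjects randomised to LY in Period 1 with placebo subjects who switch to LY at Week 12. SAP Table AMAG.6.5 shows it as a single treatment column with no group comparison.

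For treatment-emergent abnormal laboratory and vital-sign results, SAP Table AMAG.6.4 gives this population two baselines:

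- **Randomised to LY (row 4a.2):** "Baseline will be all scheduled and unscheduled measurements recorded during the baseline period as defined above (4a.1" of the same table. Table AMAG.6.2 starts that period at consent and ends it "Prior to Visit 2 dose date/time. If dose date is missing, the last date at Visit 2 will be used".
- **Randomised to placebo (row 4a.2):** "The last non-missing assessment (scheduled or unscheduled) recorded prior to the first dose of Period 2 LY study treatment".

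Row 4b.2, which adds follow-up, repeats the split.

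The definitions that use these baselines are written for a set of values:

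- SAP 6.14.3 counts a laboratory shift to low in subjects "whose minimum baseline result is normal or high and whose minimum treatment result is low". High shifts use the maximum instead.
- SAP 6.14.4 requires this transition in a vital sign: "greater than or equal to the low limit at all baseline visits to a value less than the low limit at any time", subject to a change criterion. Change is measured from the baseline minimum, or from the maximum for increases.

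Both summaries are planned for Safety Population All LY.

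**The concern.** Two subjects with the same readings are classified differently according to their Period 1 randomisation, and both are counted in the same percentage. An intermittent abnormality that predates LY removes an LY-randomised subject from the count if it appeared at any baseline reading. In an ex-placebo subject it does so only if it was present at the last reading. SAP 6.14 says the descriptive displays for this population serve to identify potential safety signals. Part of the All LY rate would then reflect the baseline rule and not the drug. The table itself would not show how much.

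**Working it through.** The plan states no figure for this point. The check applies its rules to identical data and then sizes the gap with an illustrative model.

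**1. How many baseline values each group has.** In the protocol Schedule of Activities, chemistry/hematology, blood pressure and pulse are collected at V1 and V2, so an LY-randomised subject normally has two scheduled values plus any unscheduled ones. An ex-placebo subject has the same tests at V6 and V7 and none scheduled at V8. Row 4a.2 keeps only the last value.

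**2. Laboratory patterns, each followed by an abnormal value on LY.**

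| Earlier, last pre-LY value | All-values rule (LY-randomised) | Last-value rule (ex-placebo) |
|---|---|---|
| normal, normal | counted | counted |
| abnormal, normal | not counted | **counted** |
| normal, abnormal | not counted | not counted |
| abnormal, abnormal | not counted | not counted |

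**3. Vital signs.** Table AMAG.6.12 defines low systolic pressure as 90 mm Hg or below with a fall of at least 20.

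- Readings 92 and 112 before LY, 88 on LY: the fall from the minimum is 92 − 88 = 4 (not counted); the fall from the last value is 112 − 88 = 24 (counted).
- Readings 88 and 115, then 88: the LY-randomised subject leaves the denominator because one baseline value is below the limit. The ex-placebo subject stays in and is counted, with a fall of 115 − 88 = 27.

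**4. Direction.** The last value is never below the minimum or above the maximum. Every event counted under the all-values rule is therefore also counted under the last-value rule. The mixed rule can only add ex-placebo events.

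**5. Size.** Allocation is 2:1:1:2 of about 180: 180 × 4/6 = 120 on LY and 180 × 2/6 = 60 on placebo, so ex-placebo subjects are up to one third of the column.

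Assumptions not in the documents: no drug effect; a mean chance m of an abnormal reading of 3%, 5% or 10%; within-subject correlation ρ of 0.1, 0.3 or 0.5 (beta-binomial); n = 10 post-baseline readings in both groups; two baseline readings for LY-randomised and one for ex-placebo subjects.

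With s = 1/ρ − 1, a = ms, b = (1 − m)s and B the beta function:

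- P(normal at k baseline readings) = B(a, b + k)/B(a, b)
- P(normal at baseline and abnormal later) = [B(a, b + k) − B(a, b + k + n)]/B(a, b)
- reported percentage = the second divided by the first, which is the SAP's baseline-normal denominator.

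At m = 5%, ρ = 0.3:

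| | Normal at baseline | Counted | Percentage |
|---|---|---|---|
| LY-randomised (120) | 120 × 0.917 = 110.0 | 15.4 | 14.0% |
| Ex-placebo (60) | 60 × 0.950 = 57.0 | 9.3 | 16.3% |
| Pooled, mixed rule | 167.0 | 24.7 | 14.8% |
| Pooled, all-values rule for everyone | – | – | 14.0% |

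Over the nine combinations of m and ρ, the ex-placebo to LY-randomised ratio is 1.05 to 1.25. About 0.7 to 3.6 extra ex-placebo subjects of 60 are counted per analyte. The pooled percentage is about 0.4 to 1.4 points higher than under a uniform rule.

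**6. Unequal follow-up.** LY-randomised subjects also have on-LY chemistry at V4, V6 and V7. Repeating the grid with more readings for them gives:

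| Readings (LY-randomised vs ex-placebo) | Ratio | Pooled percentage, mixed minus uniform rule |
|---|---|---|
| 13 vs 10 (chemistry through Week 52) | 0.90 to 1.11 | 0.4 to 1.3 points |
| 27 vs 24 | 0.99 to 1.14 | 0.4 to 1.3 points |

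The last row is close to the chemistry schedule through V31: V4, V6 and V7, then V9–V18, then V19–V31, or 3 + 10 + 13 = 26 against 23.

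**The case against.** **The sponsor may already have this in hand.** The introduction to SAP 6.1.4 allows an alternative baseline after the first interim lock. Its example gives ex-placebo subjects a pre-LY interval as long as screening. This shows that the need for a comparable window was seen. It remains optional, its example is Safety Population Period 2, and it leaves rows 4a.2 and 4b.2 unchanged. It would also often not restore a second value. Twenty-eight days back from V8 (Days 86–92) starts at Days 58–64, while V6 is Day 57 ± 3, so the window would usually hold only V7.

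**The consequence is small.** This stands. The column is descriptive, and the placebo-controlled Period 1 comparison is untouched.

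**The net difference between the groups is not known.** This stands too. Longer observation on LY pushes the other way, and in step 6 some ratios fall below 1. A reader might infer that ex-placebo subjects will show the higher rate in the data; the documents do not support that. What survives is the comparison of the mixed rule with a uniform one.

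Three further readings are tempting and should not be made:

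- **Inflation by 1/(1 − q).** If each reading is abnormal with constant chance q, one baseline value gives a chance of being counted 1/(1 − q) times that with two. That divides by all subjects. The SAP's denominators are restricted to subjects normal at baseline, so under constant q the factor cancels and the ratio is exactly 1. A gap needs risk to vary between subjects, as in step 5.
- **Inflated hepatic rates.** SAP 6.14.8.1 says "Maximum baseline will be the maximum non-missing observation in the baseline period", but this only sorts subjects into baseline subsets. The rates for all subjects with a post-baseline value do not depend on baseline. Only subset membership can shift.
- **The same error in rows 2.2 and 3.2.** Each uses the last value for everyone in its population, so it is internally uniform. The minimum or maximum of one value is that value, so the definitions can still be programmed.

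**Conclusion.** The inconsistency in rows 4a.2 and 4b.2 is real and follows from the text alone. Identical readings are counted differently within one pooled percentage, and the last-value rule can only add ex-placebo events relative to the all-values rule. Under the stated assumptions the pooled percentage rises by about 0.4 to 1.4 points, with equal or unequal follow-up. The abnormality rates, correlations and reading counts are illustrative, so this indicates the order of size and does not forecast any analyte.

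The point is confined to treatment-emergent abnormal laboratory and vital-sign results in the All LY column. Rows 4a.3 and 4b.3 (change from last baseline) use a last scheduled value in both groups and are consistent. No test or primary result is affected. The repair is desirable and not critical. One limit: the All LY column label in Table AMAG.6.5 carries an asterisk whose footnote is not in the text available for this review.

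**What to change.** In rows 4a.2 and 4b.2, define one baseline set for both groups. For example, use the last two scheduled assessments before the first LY dose, plus every unscheduled value from the first of these up to that dose. For laboratory tests, blood pressure and pulse this means V1–V2 for LY-randomised subjects, and V6–V7 with unscheduled values through to the V8 dose for ex-placebo subjects. Weight is also scheduled at V8 before dosing, so its last two values would be V7 and V8. Running the window to the dose keeps any unscheduled value after V7, which may be the closest pre-LY measurement. Then state that the minimum and maximum definitions in 6.14.3, and the requirement in 6.14.4 to be "greater than or equal to the low limit at all baseline visits", apply to that set.

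The cost is a few lines of SAP text and minor reprogramming on data already scheduled for collection. Slightly fewer ex-placebo subjects will qualify as normal at baseline: in the worked case, about 60 × 0.917 = 55.0 in place of 57.0.

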6.1.5. Treatment Groups by Analysis Population and Analysis Period

Table AMAG.6.5 provides the treatment groups to be displayed for each analysis population and analysis period.

Table AMAG.6.5. Treatment Groups by Analysis Population and Analysis Period

Analysis Population	Analysis Period	Treatment Groups	Treatment-Group Comparison, When Applicable
ITT, mITT, Safety Population Period 1	Period 1	
 • PBO • 200 mg IV • 600 mg IV • 1000 mg IV • All LY • Total 	For ITT and mITT: 
 • 200 mg IV vs PBO • 600 mg IV vs PBO • 1000 mg IV vs PBO For Safety Population Period 1: 
 • All LY vs PBO
EHO Group 2, EHO Group 3	Periods 1, 2, 3 and f/u (where applicable)	
 • 200 mg IV/200 mg IV • 600 mg IV/600 mg IV • 1000 mg IV/1000 mg IV • LY IV/300 mg SC • 1000 mg IV for subjects showing no improvement[#] in SES-CD from baseline at Week 12 • Placebo/1000 mg IV • Total 	N/A
Safety Population Period 2	Period 2	
 • 200 mg IV/200 mg IV • 600 mg IV/600 mg IV • 1000 mg IV/1000 mg IV • LY IV/300 mg SC • 1000 mg IV for subjects showing no improvement[#] in SES-CD from baseline at Week 12 • Placebo/1000 mg IV • All LY IV • Total 	N/A
Safety population All SC LY	All treatment periods where LY SC is administered (time during either Periods 2-3)	
 • 300 mg SC * 	N/A
Safety Population All LY	All treatment periods where LY (IV or SC) is administered	
 • LY Treatment * 	N/A

Treatment Groups by Analysis Population and Analysis Period

Analysis Population	Analysis Period	Treatment Groups	Treatment-Group Comparison, When Applicable
Safety Population All LY	All treatment periods where LY (IV or SC) is administered and Follow-Up Period	
 LY Treatment and after * 	N/A

Abbreviations: EHO = efficacy and health outcomes; f/u = follow-up; ITT = intent to treat; IV = intravenous; mITT = modified intent to treat; N/A = not applicable; PBO = placebo; SC = subcutaneous; SES-CD = Simple Endoscopic Score for Crohn's Disease.

